14.3.1. General Aspects

All clinical and safety data collected for the VITDALIZE trial will be analysed with SAS v9.4 procedures. Data will be presented as summary tables and, where appropriate, as plots. Continuous data will be described by means, standard deviations, medians and upper and lower quartiles unless otherwise stated. The number of observations and minimum and maximum values will also be included. All descriptive summaries will be displayed to 1 more decimal place than actually measured. Categorical data will be summarized using frequencies and percentages.

14.3.2. Demographic and Baseline Characteristics

A summary of demographic, baseline and diagnostic characteristics, including relevant medical history will be presented by treatment groups using appropriate descriptive and inferential statistics.

14.3.3. Primary Outcome Measure

The primary outcome, 28-day mortality will be displayed using Kaplan Meier estimates of survival curves in each treatment. A mixed effects Cox Proportional Hazard model including

centre as a random effect will be fitted to obtain an adjusted hazard ratio and 95% confidence interval. For the UK arm only, a complier average causal effect (CACE) analysis will also be performed for the primary outcome. Details of the primary outcome analysis will be defined in the SAP approved by the Sponsor and approved by the international DMC prior to any interim analysis. The UK specific outcomes will be defined in a separate SAP that will describe all of the statistical analysis that will be undertaken for the UK arm only and appended to the Sponsor approved SAP.

14.3.4. Secondary Outcome Measures

ICU, hospital mortality, 90-day mortality and 1-year mortality will be analysed using the same methods as described for the primary outcome. For any other secondary outcomes that are continuous, these will be analysed using mixed effects linear regression model. The safety outcomes, (hypercalcemia on day 5, new kidney stones, self-reported falls, and fractures until day 90) will be analysed as binary variables and compared using a mixed effects binomial model.

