- Trial medication compliance
- If applicable¹, patient health related quality of life (EQ-5D-5L and WHODAS 2.0, proxy if patient does not have capacity)
- If applicable¹, health economics questionnaire

Day 90 marks the end of the trial intervention.

1 year

- Survival status
- If applicable¹, patient health related quality of life (EQ-5D-5L and WHODAS 2.0, proxy if patient does not have capacity)
- If applicable¹, health economics questionnaire

Information obtained at day 28, 90 and 1 year (see above) can be obtained from the hospital's data management systems or via telephone interview with the trial patient or delegated family member. Additional information will be obtained from reviewing hospital clinical records and via NHS Digital and if applicable¹, patient Health economics questionnaire.

The following questionnaires will not be collected for patients recruited post substantial amendment 5 (SA5) implementation:

- EQ-5D-5L
- WHODAS 2.0
- Health economics questionnaire

¹ Only applicable if patient recruited pre-SA5 implementation

² Only applicable if patient recruited pre-SA5 implementation and consents to the sub-study

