8.2. Secondary Outcomes

- 90 day and 1-year mortality
- ICU and hospital mortality
- Hospital and ICU length of stay (starting at day 0, ending at discharge from the trial site or day 90 or mortality, whichever occurs first)
- Change in organ dysfunction on day 5 as measured by Sequential Organ Function Assessment score (SOFA), number of organ failures (0-6; defined as > 2 SOFA points in each of the 6 categories)
- Hospital and ICU readmission until day 90
- Discharge destination (home, rehabilitation, other hospital)
- Katz Activities of Daily Life at day 90
- Self-reported infections requiring antibiotics until day 90
- Health-related quality of life (EQ-5D-5L) at 90 days and 1 year¹
- Disability assessment (WHODAS 2.0) at 90 days and 1 year¹
- Secondary health care utilisation in the first year (ICU and hospital length of stay, readmissions and utilisation of hospital and community care resources after hospital discharge 1 year after randomisation), from Hospital Episode Statistics, civil registry data held by NHS Digital and patient questionnaires¹
- Health economics analysis¹
 - Cost effectiveness of screening for and treating VDD in critical illness
 - Cost per quality-adjusted life year gained 1 year after randomisation and at end of life

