14.2. Analysis of Outcome Measures

A separate Statistical Analysis Plan (SAP) will be produced by the Sponsor outlining the analysis of VITDALIZE, the UK specific outcomes will be appended to the SAP completed by the UK Statistician in collaboration with the UK CI. The SAP will provide a more comprehensive description of the planned statistical analyses. A brief outline of these analyses is given below. The primary comparison groups will be composed of those treated with vitamin D3 versus those treated with placebo.

Intention-to-treat (ITT) population: The primary analysis will be performed on the ITT population. The ITT population will include all patients who receive at least the loading dose of the trial medication. All patients included here will be analysed according to the treatment assignment during randomisation.

Per protocol population: The per protocol population will include all patients who received the loading dose and have a compliance >80%. Compliance is defined as self-reported percentage of doses ingested until day 90. Other protocol violations may also lead to exclusion of patients from the per protocol population. This will be discussed on an individual basis within the international trial's teams working on VITDALIZE.

Safety population: The safety analyses will be based on the treated set, which is defined as all randomised patients who receive at least 1 dose of trial medication. All patients will be analysed according to the treatment they received.

All available data will be used in the analyses and data summaries. There will be no imputation of any missing data. All outcomes will be adjusted for the baseline values (where available) and the stratification parameters (gender and centre). If covariate adjustment is not practical, then unadjusted estimates will be produced and it will be made clear in the output why this occurred, e.g. due to lack of model convergence.

14.3. **Data analysis**

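### ICU and hospital mortality are assigned Kaplan-Meier curves and a Cox model, with no horizon and no rule for live discharge, which is a competing event

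*Protocol*

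**What the plan says.** Section 14.3.4 (Secondary Outcome Measures) puts four mortality outcomes under one method: "ICU, hospital mortality, 90-day mortality and 1-year mortality will be analysed using the same methods as described for the primary outcome". Section 14.3.3 (Primary Outcome Measure) defines that method. The display is that "28-day mortality will be displayed using Kaplan Meier estimates of survival curves in each treatment", and the estimate comes from a mixed-effects Cox model in which "centre as a random effect will be fitted to obtain an adjusted hazard ratio and 95% confidence interval".

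Section 8.2 lists the two outcomes only as "ICU and hospital mortality", with no time limit. The nearest thing to an end rule is in the next item, length of stay, which is counted as "ending at discharge from the trial site or day 90 or mortality, whichever occurs first". That rule is not attached to mortality. Section 8.2 also lists another hospital among the discharge destinations. Survival status is followed after discharge: under section 8, the day 28, day 90 and 1-year information "can be obtained from the hospital's data management systems or via telephone interview with the trial patient or delegated family member". Section 14.2 calls the text a brief outline and adds: "The SAP will provide a more comprehensive description of the planned statistical analyses". The SAP was not available for this review.

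**The concern.** Mortality at 28 days, 90 days and 1 year has a fixed horizon and counts death wherever it happens, so Kaplan-Meier and Cox suit it. ICU and hospital mortality are different. Once a patient leaves alive, the event can no longer occur. Kaplan-Meier with discharge censored assigns discharged patients the death risk of those who remain, and so estimates mortality as if nobody could leave. Its complement then exceeds the proportion who actually die there.

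The treatment contrast is also open to misreading. Shorter ICU and hospital stay is one of the trial's own objectives (section 2.1), so the discharge rate may differ between arms. A hazard ratio among patients still in the unit and a ratio of the proportions dying there can then tell different stories. The signal that motivated the trial was given as proportions dying in hospital in the severe-deficiency subgroup of VITdAL-ICU, 28.6% against 46.1% (section 1.2), so the proportion is the quantity readers will look for.

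**Working it through.** **The plan's own figures.** The protocol gives no figure for ICU or hospital mortality. Its sample size concerns 28-day mortality and reproduces: ln(0.80)/ln(0.75) = 0.776 (stated 0.78), with 487 events by Schoenfeld's formula (stated 486). Nothing below bears on it.

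**Assumptions, not in the protocol.** Constant hazards of in-hospital death and of live discharge; a median time to death or discharge of m = 10 to 30 days; a final proportion p dying in hospital. I take p = 25%, borrowing the control 28-day rate in section 14.1 as a round figure.

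**Formulas.** Total exit hazard λ = ln 2 / m; death hazard pλ; discharge hazard (1 − p)λ.

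- True cumulative incidence of in-hospital death by day t: p(1 − e^(−λt)).
- One minus Kaplan-Meier with discharge censored: 1 − e^(−pλt).

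Example, m = 14 and t = 90: λt = 0.0495 × 90 = 4.456. True: 0.25 × (1 − e^(−4.456)) = 24.7%. Kaplan-Meier: 1 − e^(−1.114) = 67.2%.

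| Median stay (days) | True, day 28 | 1 − KM, day 28 | True, day 90 | 1 − KM, day 90 |
|---|---|---|---|---|
| 10 | 21.4% | 38.4% | 25.0% | 79.0% |
| 14 | 18.8% | 29.3% | 24.7% | 67.2% |
| 20 | 15.5% | 21.5% | 23.9% | 54.1% |
| 30 | 11.9% | 14.9% | 21.9% | 40.5% |

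With p = 46.1%, the placebo figure from VITdAL-ICU, the day-90 values are 40–46% true against 62–94% by Kaplan-Meier.

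**Contrast between arms, same exit hazard.** For p = 25% against 20% with the same m in both arms, the day-90 risk difference is 4.4–5.0 points in truth and 6.5–8.2 points on the Kaplan-Meier scale. The cause-specific hazard ratio is 0.20λ/0.25λ = 0.80, equal to the ratio of true risks. So the hazard ratio does not always mislead.

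**Contrast between arms, discharge rate changed by treatment.** Take m = 14 and p = 25% in controls: death hazard 0.25 × 0.0495 = 0.0124 per day, discharge hazard 0.0371 per day. Keep the death hazard equal in both arms and multiply the treated discharge hazard by 1.25, giving 0.0464. Treated in-hospital mortality by day 90 is 0.0124/(0.0124 + 0.0464) × (1 − e^(−0.0588 × 90)) = 20.9%, against 24.7% in controls. The cause-specific hazard ratio is 1.00 and both Kaplan-Meier curves reach 67%. With multipliers of 1.15 and 1.5, treated mortality is 22.3% and 18.1%; with slower discharge (0.9 and 0.8) it is 26.6% and 28.7%. The hazard ratio stays at 1.00 throughout.

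**The other reading.** If every patient discharged alive is kept in the risk set as event-free to a common horizon, and nobody is otherwise censored, one minus Kaplan-Meier equals the cumulative incidence and there is no bias.

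**The case against.** The strongest reply is that the protocol never says discharged patients are censored. A reader might infer it from the word-for-word transfer of the primary method, or from the length-of-stay rule next to it, but no sentence states it. A fixed-horizon reading fits the text and is unbiased, and the protocol defers detail to the SAP. This stands: the protocol cannot be said to make the censoring error. What remains is that it names a method for outcomes that need a further rule, and two permissible readings answer different questions.

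Two other strong readings also fail.

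- One might infer that a real fall in hospital mortality would be reported as no effect. That needs equal death hazards in both arms, which the example imposes. If treatment lowers the death hazard, the cause-specific hazard ratio falls below 1 and is valid as such. Evidence for faster discharge is also weak here: section 1.2 reports that VITdAL-ICU found no difference in length of hospital stay.
- One might infer that the result could not be compared with VITdAL-ICU. Section 14.3.1 has categorical data summarised as frequencies and percentages, so crude proportions can be expected. Section 1.2 also gives that trial's effect as 0.56 without naming the measure. The proportions imply a risk ratio of 0.62 and an odds ratio of 0.47, while ln(0.714)/ln(0.539) = 0.55, so a hazard ratio is plausible there.

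**Conclusion.** The point holds in limited form. Section 14.3.4 applies Kaplan-Meier and Cox to two outcomes for which live discharge is a competing event, without a horizon or a rule for discharge. If discharge is censored, the curves overstate in-hospital mortality substantially, by roughly 19 to 54 percentage points at day 90 across the assumed stays (40.5 − 21.9 and 79.0 − 25.0). The hazard ratio could not then be read as the effect on the proportion dying in the ICU or hospital. These sizes rest on constant hazards, an assumed final mortality of 25% and assumed median stays of 10 to 30 days; the direction of the overstatement does not.

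This is a moderate issue on secondary outcomes, not one that must be settled for the trial to be sound. The primary outcome, 90-day and 1-year mortality and the sample size are untouched.

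**What to change.** In section 14.3.4, separate ICU and hospital mortality from the fixed-horizon outcomes. Define each as death before live discharge, yes or no, up to a stated horizon; the day 90 already used for length of stay would serve. Analyse both with the mixed-effects binomial model that the section already names for safety outcomes, adjusted for sex and centre. Where curves are shown, use cumulative incidence with live discharge as the competing event. State whether transfer to another hospital ends the stay or continues it. Keep Kaplan-Meier and Cox for 28-day, 90-day and 1-year mortality.

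The cost is a few sentences in the protocol and matching text in the SAP, agreed before unblinding so that the choice between readings is not made with results in view. No new data are needed if the stay ends at discharge from the trial site, as it does for length of stay. Counting through a transfer would depend on what the receiving hospital returns.

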14.3.5. Subgroup Analyses

The effect of high dose vitamin D versus placebo will be evaluated in the following *a priori* subgroups: i) patients with sepsis (admission diagnosis) vs non-sepsis (based on the evidence that vitamin D has antimicrobial properties that may benefit this population in particular (16); ii) kidney function, CKD 4 (eGFR<30mL/min/1.73m2) or lower vs higher (based on the possible effect of pre-existing CKD and VDD on increased mortality and alternate metabolism of vitamin D3 (cholecalciferol); iv) COVID-19 or Non-COVID-19 patients.

14.3.6. Missing Data and Sensitivity Analyses

Every attempt will be made to collect full follow-up data on all trial patients; it is thus anticipated that missing data will be minimal. There will be no imputation of missing data for the purpose of the trial.

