14. STATISTICAL CONSIDERATIONS

14.1. Sample Size

The sample size for the multinational trial is based on the primary endpoint 28-day mortality. In the VITdAL-ICU trial, in the pre-defined subgroup with severe VDD, 28-day mortality rates of 36% (37/102) in the placebo group and 20% (20/98) in the vitamin D group were observed (51). The VITDALIZE trial has been designed to be powered to detect a smaller, but clinically relevant absolute mortality difference of 5% with a power of 80% or a 6% difference with 90% power with an assumed baseline mortality rate of 25% (close to the lower limit of the 95% CI of the 36% mortality observed in VITdAL-ICU). This corresponds to a clinically important relative risk reduction of between 20% and 24%. Using a fixed sample size design and a 2-sided log-rank test for equality of survival curves with a 2-sided alpha level of 5%, a sample size of over 1000 patients per group will be needed (total sample size of approximately 2200). The table below shows this, and varies the baseline event rate from 25% to 30% to illustrate that our assumptions are robust to modest variations in our assumptions.

Placebo 28-day all-cause mortality	25%		30%	
	80% power	90% power	80% power	90% power
VitD 28-day all-cause mortality	20%	19%	25%	24%
Hazard ratio	0.78	0.73	0.81	0.77
N = (per group)	1093	1002	1248	1149
Total number of events required	486	434	686	620
N = (total)	2186	2004	2496	2298

Accounting for a drop-out rate of approximately 10% yields a total sample size of N=2400 patients with the UK contributing 25% of the sample size with 600 patients. Loss to follow up in critical care trials for 28-day mortality is low and is approximately 3% in previously published critical care trials (51, 56, 57) so this 10% estimate of loss to follow up is also conservative.

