14.6.1. Within trial analysis

The within trial analysis will use the data collected within the trial, and so estimates of costs and benefits will relate to the initial period of 28 days, to reflect the primary outcome for the trial. Further analyses of costs and outcomes will be undertaken at 90 days and 12 months, based on the secondary outcomes associated with the trial. The data used for this analysis will primarily be the trial-specific resource use data and costs. The initial economic analysis will assess cost-effectiveness based on incremental cost per life gained at 28 days and 90 days reflecting the primary outcome of the trial. A secondary analysis of incremental cost per QALY gained over a 12-month period will also be undertaken in line with NICE recommendations. Initially, the base case analysis will be framed in terms of a cost-consequences analysis for the trial arms, and data will be reported in a disaggregated manner on the incremental cost and important consequences assessed in the trial.

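### The blanket no-imputation rule makes no exception for the UK economic evaluation and, read literally, bars multiple imputation of EQ-5D-5L, WHODAS 2.0 and cost data

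*Protocol*

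**What the plan says.** The rule appears twice in the protocol. Section 14.2 (Analysis of Outcome Measures) says: "All available data will be used in the analyses and data summaries. There will be no imputation of any missing data". Section 14.3.6, headed "Missing Data and Sensitivity Analyses", first expects full follow-up, so that "it is thus anticipated that missing data will be minimal", and then closes with "There will be no imputation of missing data for the purpose of the trial". It names no sensitivity analysis. Section 14.2 also says that "The SAP will provide a more comprehensive description of the planned statistical analyses".

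Section 14.1 sets the sample size: "Accounting for a drop-out rate of approximately 10" per cent, the total becomes 2400. It adds that loss for 28-day mortality in earlier critical care trials was about 3%, and calls the 10% conservative.

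Section 14.6.1 plans, after cost per life gained at 28 and 90 days, "A secondary analysis of incremental cost per QALY gained over a 12-month period". Section 14.5 collects EQ-5D-5L at baseline, 28 days, 90 days and 1 year, and NHS and social care use by questionnaire at 28 days, 90 days and 12 months. Screening, treatment and length-of-stay data come from trial reporting, and secondary care use from Hospital Episode Statistics. Section 11.2 lets patients or their representatives decline any or all questions and provides for proxy completion. Sections 8 and 8.2 stop EQ-5D-5L, WHODAS 2.0 and the health economics questionnaire for patients recruited after SA5.

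**The concern.** The protocol does not leave the missing-data method open; it prohibits one. The prohibition is unqualified, so an analysis plan that multiply imputed utilities or costs would contradict the protocol.

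The economic evaluation is where this matters. A patient's 12-month QALY is an area under four utility values, so one missing value leaves it undefined unless some method handles the gap. Sections 14.5 and 14.6 name none. The deterministic and probabilistic analyses planned under the presentation of results address parameter uncertainty, not missing responses.

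Patients are recruited critically ill and may be unable to answer, so non-response is likely to depend on health. A complete-case analysis discards partial records and over-represents patients well enough to respond. If non-response differs by arm, the incremental QALY and cost are biased as well.

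A smaller point concerns mortality. A tipping-point analysis assigns outcomes to patients of unknown status, so a literal reader could think the rule forbids that too.

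**Working it through.** **1. The plan's own figures.** Inputs from section 14.1: 25% vs 20% mortality, 80% power, two-sided 5%, 1:1 allocation.
- Hazard ratio = ln(0.80)/ln(0.75) = 0.776 (stated 0.78).
- Freedman: 492 events, 1094 per group. Schoenfeld: 487 events, 1083 per group. Stated: 486 events, 1093 per group.
- Drop-out: 2186/0.90 = 2429, or 2186 x 1.10 = 2405. Stated: 2400.

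These agree to within 3%, so no stated figure is wrong here.

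**2. Share of patients with a complete QALY.** The documents give no completion rates. Assumptions: completion r per visit of 70%, 80% or 90%, independent across visits; 22.5% dead by day 28, the mean of 25% and 20%; no later deaths. A patient who dies before day 28 needs only the baseline questionnaire, because utility after death is known. A survivor needs all four.

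Complete share = 0.775 x r^4 + 0.225 x r
- r = 0.7: 0.775 x 0.240 + 0.225 x 0.7 = 0.186 + 0.158 = 0.34
- r = 0.8: 0.775 x 0.410 + 0.225 x 0.8 = 0.317 + 0.180 = 0.50
- r = 0.9: 0.775 x 0.656 + 0.225 x 0.9 = 0.508 + 0.203 = 0.71

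Independence is pessimistic. If the same patients missed every visit, the share would simply be r (70-90%). Later deaths would also raise it.

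**3. Mortality: extreme bounds.** Take 25% vs 20% among patients followed, and a fraction m lost per arm. The difference (placebo minus vitamin D) then lies between 0.05 x (1 - m) - m and 0.05 x (1 - m) + m.
- m = 0.03: 0.0485 - 0.03 = 1.85 points, to 0.0485 + 0.03 = 7.85 points
- m = 0.10: 0.045 - 0.10 = -5.5 points, to 0.045 + 0.10 = 14.5 points

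**4. Mortality: tipping point.** This uses 1200 per arm, a two-proportion z-test as a stand-in for the log-rank test, and 25% mortality among lost placebo patients. Placebo deaths then total 300 of 1200 in each case below. Significance at 5% is lost when vitamin D deaths reach 260 of 1200: difference 0.0333, standard error 0.0173, z = 1.93.

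| Loss per arm | Lost | Vitamin D deaths among followed | Deaths needed among lost | Mortality among lost |
|---|---|---|---|---|
| 3% | 36 | 233 | 27 | 75% |
| 5% | 60 | 228 | 32 | 53% |
| 10% | 120 | 216 | 44 | 37% |

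**The case against.** The strongest reply is that the SAP is not shown and the protocol defers detail to it. For sensitivity analyses this stands: their absence from the protocol, even under a heading that mentions them, is no error. It does not answer the prohibition, which the SAP cannot lift without contradicting the protocol.

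A reader might infer that the mortality result is left untested against loss to follow-up. The documents do not support that. The primary analysis is a Cox model, which keeps patients until censoring. Expected 28-day loss is about 3%. Vital status can come from hospital systems, patient or family contact, clinical records or NHS Digital (section 8), and two of the three withdrawal types in section 8.6 keep follow-up through central NHS bodies. At 3% loss even the extreme bounds stay positive.

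A reader might also infer that the rule forces complete-case QALYs. It does not: section 14.2 promises to use all available data, and likelihood-based or weighted analyses need no imputation. The rule also sits in 14.2 and 14.3, so its reach into 14.4 to 14.6 follows from its unlimited wording, not from an explicit statement. What remains is that multiple imputation is excluded on a literal reading and nothing is named in its place.

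Finally, raising 80% to the fourth power gives 41% complete. That overstates the loss, because patients who die need no later questionnaires; 50% is the corrected figure. Proxy completion and routine data reduce the problem further but do not remove it.

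**Conclusion.** The point holds for the economic and questionnaire outcomes. The protocol fixes an unqualified no-imputation rule, makes no exception for the UK evaluation and names no other way to handle missing EQ-5D-5L, WHODAS 2.0 or cost data. On the stated assumptions, a complete-case QALY analysis would use about half the patients at 80% completion per visit (34-71% for 70-90%). These shares are illustrative: they rest on assumed completion rates, independence across visits and no deaths after day 28.

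For mortality the point is only one of clarification. At the expected 3% loss, about 75% mortality among lost vitamin D patients against 25% among lost placebo patients would be needed to overturn a 5-point difference. At the budgeted 10%, about 37% against 25% would do so. A tipping-point check is cheap, and the wording should not appear to forbid it.

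EQ-5D-5L not collected after SA5 is missing by design and is a separate matter. The change is worth making, but it does not threaten the primary analysis.

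**What to change.** Amend sections 14.2 and 14.3.6, and add a sentence to 14.6:
- Limit the no-imputation rule to the primary available-data Cox analysis.
- For patients recruited before SA5, use multiple imputation by arm for missing EQ-5D-5L, WHODAS 2.0 and costs. Set utility to 0 after death rather than imputing it, and report complete-case results as a sensitivity analysis.
- State that questionnaires not collected after SA5 are missing by design and are not imputed under this provision.
- State that the rule does not bar a tipping-point sensitivity analysis for unknown 28-day status; its details can stay in the SAP.

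The cost is protocol and SAP wording and modest extra analysis. The downside is that the imputation model must be pre-specified. Multiple imputation also rests on its own assumption about why data are missing, which is why the complete-case result should stay alongside it.
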